8. METHODS

8.1 Study parameters/endpoints

8.1.1 Main study parameter/endpoint

In order to gain insight into the volume and intensity of physical activity, both the wrist-worn GENEActiv triaxial accelerometer and the thigh-worn Axivity AX3 Logging tri-axial accelerometers will measure physical activity energy expenditure (PAEE) (7) and the intensity distribution of PAEE (7),(8). The wrist worn GENEActiv triaxial accelerometer will additionally measure the participants' step count (28),(35).

8.1.2 Secondary study parameters/endpoints

Prior to wearing the accelerometers we will ask the participants to complete a total of four questionnaires:

1. A Dutch version of the International Physical Activity Questionnaire - Short Form (IPAQ-SF) (36),(37),(38),(39),(40). This is a self-reported physical activity questionnaire. This questionnaire can be found in Appendix A.
2. A validated Dutch version of the Short Questionnaire to Assess health-enhancing physical activity (SQUASH). This is also a self-reported physical activity questionnaire. This questionnaire can be found in Appendix B.
3. A psychometrically sound Dutch version of the EQ-5D-5L (41),(42),(43),(44),(45). This questionnaire evaluates health status in the five dimensions of mobility (ability to walk about), self-care (ability to take care of personal hygiene and activities of daily living), usual activities (ability to perform usual activities, such as work, study, housework, family or leisure activities), pain/discomfort and anxiety/depression. This questionnaire can be found in Appendix C.
4. Finally, we will ask the participants to complete a validated Dutch version of the The Oxford Hip Score (OHS).(46),(47),(48),(49) This questionnaire includes 12 questions about the patient's ability to perform specific activities such as walking, climbing stairs, and putting on shoes and socks, as well as their experience of pain and limitations in daily activities due to their hip condition. This questionnaire can be found in Appendix D.

8.2 Randomisation, blinding and treatment allocation

In this observational (follow-up) study participants will not be randomised, blinded or treated. The potential participants for this current study have previously participated in a randomised controlled trial. In this RCT (34), a total of 82 patients were randomly assigned to receive resurfacing hip arthroplasty (RHA, $n = 34$) with a 6-mm thick cobalt-chromium cup or conventional total hip arthroplasty (THA, $n = 26$) with a more conical threaded titanium cup. All participants of this previous RCT will be contacted to ask if they are willing to participate in this follow-up study.

8.3 Study procedures

8.3.1 Wearing GENEActiv Triaxial Accelerometer & Axivity AX3 Logging Triaxial Accelerometers

Participants in this study will be sent both accelerometers by post. Participants will be asked to wear both the GENEActiv triaxial accelerometer for ten days and nights on their non-dominant wrist and the Axivity AX3 Logging tri-axial accelerometer on their surgical thigh for 48 hours, respectively. Both accelerometers are programmed to start at a certain time. The accelerometers are waterproof and should be worn continuously including during showering and sleeping. After use, the participants are requested to return both accelerometers to the researcher into a padded pre-paid envelope as soon as possible so the researcher can download the data. The envelope can be posted into a normal post box.

8.3.2 Instructions for wearing the accelerometers

We will provide all participants with an instruction leaflet explaining how the accelerometers should be used. This leaflet also contains a weblink to a video explaining how to wear the accelerometer: www.mrc-epid.cam.ac.uk/geneactiv1. Although this video is in English, in combination with the Dutch written instructions these should be easy to understand. The instruction leaflet also contains a phone number that participants can call in case they have questions or need assistance in placing or using the accelerometers.

8.4 Withdrawal of individual subjects

Subjects can leave the study at any time for any reason if they wish to do so without any consequences. The investigator can decide to withdraw a subject from the study for urgent medical reasons.

8.5 Replacement of individual subjects after withdrawal

N/A

8.6 Follow-up of subjects withdrawn from treatment

N/A

8.7 Premature termination of the study

N/A

9. SAFETY REPORTING**Temporary halt for reasons of subject safety**

In accordance to section 10, subsection 4 of the WMO, the sponsor will suspend the study if there is sufficient ground that continuation of the study will jeopardise subject health or safety. The sponsor will notify the accredited METC without undue delay of a temporary halt including the reason for such an action. The study will be suspended pending a further positive decision by the accredited METC. The investigator will take care that all subjects are kept informed.

9.2 (Serious) Adverse events**9.2.1 Adverse events (AEs)**

Adverse events are defined as any undesirable experience occurring to a subject during the study that is related to wearing the GENEActiv or Axivity AX3 Logging tri-axial accelerometers.

Wearing accelerometers may cause mild skin redness or irritation due to prolonged contact with the device. This is considered an expected adverse event of mild severity. Participants will be instructed to monitor their skin daily and only report signs of persisting irritation to the researcher. Mitigation strategies include the use of breathable hypoallergenic straps, participant instruction on proper device use, and how to treat the affected area with moisturising skin cream. Only severe or persistent irritation will be reported as an AE.

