4. STUDY POPULATION

We will only approach patients that have participated in a previous randomised controlled trial (34) that was conducted in Rijnstate hospital between 2007-2008. These include 34 patients after hip resurfacing and 26 patients after total hip replacement.

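### Section 9.2.1 asks participants to report only persisting skin irritation but counts severe irritation as an adverse event too, so a severe, short-lived reaction is not asked for

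*Combined protocol and SAP*

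**What the plan says.** Section 9.2.1 defines an AE broadly, as any undesirable experience related to wearing either device. It then turns to skin irritation. It describes mild redness or irritation from prolonged contact and adds: "This is considered an expected adverse event of mild severity". The next sentence is the instruction to participants: "Participants will be instructed to monitor their skin daily and only report signs of persisting irritation to the researcher". After a sentence on mitigation (straps, advice on use, skin cream), the paragraph closes with the recording rule: "Only severe or persistent irritation will be reported as an AE".

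Four other parts of the protocol bear on whether such a reaction would come to light:

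- Section 8.1.2 places the questionnaires before wear: "Prior to wearing the accelerometers we will ask the participants to complete a total of four questionnaires".
- Section 8.3.1 describes devices sent out by post, and at the end "the participants are requested to return both accelerometers to the researcher into a padded pre-paid envelope as soon as possible". No question about adverse events is described at that point.
- Section 8.3.2 says the leaflet carries a phone number for questions or for help with placing or using the devices.
- Section 11.3 discusses minor irritation and localised rash. It suggests leaving the monitor off for a night or drying the strap, and asks for the monitor to be removed and returned if the irritation continues.

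**The concern.** What participants are asked to report should cover at least what the study intends to record. Here the request is narrower than the recording rule, and the word *only* makes it a restriction rather than an incomplete list. A participant who follows the sentence exactly would not mention a severe reaction that settled once the device came off.

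This matters more than it would in a study with clinic visits. Wear takes place at home, the devices travel by post, and self-report is the only route the protocol describes by which the team would learn of a skin reaction. If the participant materials repeat the wording of 9.2.1, an event that the protocol counts as an AE would be recorded only when the participant raised it unprompted.

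**Working it through.** No arithmetic applies: the point depends on no rate, sample size or error level, and the plan gives no figure to reproduce. The check is to compare the two tests in 9.2.1, and then to look for any other step that would pick up what the first one leaves out.

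**Step 1. Compare the two tests.** The participant test is: irritation persists. The AE test is: irritation is severe, or it persists. Crossing severity with duration gives four cases.

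| Irritation | Participant asked to report? | AE under the closing rule? | Consistent? |
|---|---|---|---|
| Mild, short-lived | No | No | Yes |
| Mild, persisting | Yes | Yes | Yes |
| Severe, persisting | Yes | Yes | Yes |
| Severe, short-lived | No | Yes | **No** |

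Every case that meets the participant test also meets the AE test, but not the reverse. Exactly one case is left uncovered.

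**Step 2. Look for another step that covers that case.**

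- *Questionnaires (8.1.2).* They are completed before wear starts, so they cannot pick up a reaction to wear.
- *Return of devices (8.3.1).* Return is by post, with no AE query described.
- *Leaflet phone number (8.3.2).* A participant could use it after a severe reaction, and what was said could be recorded. It is offered for questions and practical help, and is not presented as a reporting instruction.
- *Serious adverse events (9.2.2).* Complications beyond the expected range are treated as serious on the surgeon's judgement. The investigator's duty to report starts from knowledge of the event, so this section does not widen what participants are asked to say.
- *Follow-up of AEs (9.3).* It says how long AEs are followed. I infer that this presupposes an event already known to the team.
- *Risks (11.3).* It deals with minor irritation and localised rash, and again ties action to persistence. A night without the monitor could also settle a reaction before it counted as persisting.

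None of these asks participants about severe irritation that does not persist.

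**Step 3. Size.** The documents give no frequency for severe, short-lived irritation. Without one, the number of people or days of wear would describe exposure and not the number of events missed, so I attach no figure.

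**The case against.** The strongest reply is context. The instruction directly follows the description of mild, expected irritation, and may be meant only to stop participants reporting every trace of redness. The closing sentence has a different job: it tells the study team what to record. Two sentences addressed to different people need not match word for word.

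This reading is plausible, and it is the main reason the point is minor. It does not remove the point. The text does not limit the instruction to mild irritation. If it did, the protocol would contain no participant instruction for severe irritation at all, and the same edit would be needed.

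It is also fair to say that the uncovered case is narrow. The reaction must be severe, must settle quickly, and must go unmentioned by someone who checks the skin daily. Persistence is not defined, so irritation still visible at the next daily check might qualify. A volunteered report would fall under the general AE definition. All of this stands, and it limits the size of the point.

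A reader might infer more than the documents support, in three ways:

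- *That participants are actually being told to keep quiet about severe reactions.* What they are told sits in the leaflet and in the information form (Appendix E). Neither is in the supplied text, and that absence is not a fault of the plan. Only the protocol wording can be judged.
- *That 11.3 contradicts the AE rule.* It does not. It sets no AE rule and gives sensible handling advice for minor irritation. A severity trigger for removing and returning the monitor there would be a preference, and it could cost wear data.
- *That the study's results are at risk.* Safety is not among the endpoints in 8.1.1 and 8.1.2, and the comparison of physical activity does not depend on which skin reactions are reported.

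**Conclusion.** The point holds as a small inconsistency between two rules stated in one paragraph. Read literally, 9.2.1 leaves severe, short-lived irritation as an AE that participants are not asked to report, and no other described step asks for it.

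The consequence is possible under-recording of AEs of one kind, in a study that section 13 classes as negligible risk. The affected group is probably very small, though no number can be put on it. The conclusion rests on two assumptions: that the instruction is taken as written rather than as confined to mild irritation, and, for any practical effect, that the participant materials carry the same wording. It is worth considering as an edit and no more than that.

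**What to change.** In 9.2.1, reword the instruction so that participants *report any severe or persisting irritation to the researcher*, and name the phone number already printed in the leaflet as the way to do so. Then check that the leaflet and the information form say the same, and change them only if they do not. Section 11.3 can stay as it is.

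The cost is a few words in the protocol, possibly a matching edit to the participant materials, and perhaps a few more phone calls. In return, the events that the protocol defines as AEs become the events that participants are asked to report.

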9.2.2 Serious adverse events (SAEs)

A serious adverse event is any untoward medical occurrence or effect that

- results in death;
- is life threatening (at the time of the event);
- requires hospitalisation or prolongation of existing inpatients' hospitalisation;
- results in persistent or significant disability or incapacity;
- is a congenital anomaly or birth defect; or

- any other important medical event that did not result in any of the outcomes listed above due to medical or surgical intervention but could have been based upon appropriate judgement by the investigator.

Hospital admissions, that occur between the day of signing the Informed Consent and the day the participant starts wearing the accelerometers, will not be considered an SAE.

Excessive, outside normally expected range complications will be considered as SAE as determined by the patient's primary orthopaedic surgeon. The investigator will report all SAEs to the sponsor without undue delay after obtaining knowledge of the events, except for the following SAEs. The sponsor will report the SAEs through the web portal ToetsingOnline to the accredited METC that approved the protocol, within even days of first knowledge for SAEs that result in death or are life threatening followed by a period of maximum of eight days to complete the initial preliminary report. All other SAEs will be reported within a period of maximum 15 days after the sponsor has first knowledge of the serious adverse events.

9.3. Follow-up of adverse events

All AEs will be followed until they have abated, or until a stable situation has been reached. Depending on the event, follow up may require additional tests or medical procedures as indicated, and/or referral to the general physician or a medical specialist. SAEs need to be reported till end of study within the Netherlands, as defined in the protocol.

9.4 Data Safety Monitoring Board (DSMB) / Safety Committee

N/A

10. STATISTICAL ANALYSIS

10.1 Primary study parameter(s)

Following the devices' return to the researcher, the recorded data will be downloaded and stored securely in a dedicated study folder on Rijnstate's digital network. The raw triaxial wrist and thigh acceleration data will be auto-calibrated to local gravitational acceleration (in g) and then converted to a Vector Magnitude (VM). VM, or Euclidean Norm, can be interpreted as the magnitude of acceleration the device was subjected to at each measurement, including gravitational acceleration. Non-wear detection procedures will be applied, and any such non-wear periods will be excluded from these analyses. The acceleration signal will be summarised to a common time resolution of one observation per minute and subjected to prediction models

to calculate physical activity energy expenditure, time in moderate-to-vigorous physical activity, and step count.

Raw accelerometry data will be processed using the R-project for Statistical Computing and open-source packages (R Foundation for Statistical Computing, Vienna, Austria). Statistical analysis will be conducted using STATA/SE version 17 (StataCorp, College Station, TX, USA). For descriptive statistics, we will report medians (interquartile ranges) or means (standard deviations) for continuous variables and proportions for categorical variables. To examine face validity and the performance of each multi-level linear regression model, we will conduct ANOVA repeat measures analysis to calculate Pearson's coefficient and Root Mean Squared Error metrics. Differential bias will be assessed by age, sex, and BMI categories.

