SQUASH	Short Questionnaire to Assess health-enhancing physical activity
THA	Total Hip Arthroplasty
UCLA	University of California at Los Angeles
UK	United Kingdom
WMO	Medical Research Involving Human Subjects Act; in Dutch: Wet Medisch-wetenschappelijk Onderzoek met Mensen

SUMMARY

Rationale:

Arthritis significantly impacts patients' lives, affecting everything from pain and fatigue to daily activities and overall mortality. Physical activity (PA), particularly moderate-to-vigorous physical activity (MVPA), is crucial in managing arthritis symptoms and reducing mortality risks, with even minimal MVPA providing significant health benefits. Wearable technology has revolutionized the measurement of physical activity, offering accurate, large-scale data that informs treatment efficacy. Despite this, little is known about how common arthritis treatments affect physical activity levels, highlighting a critical gap in our understanding. Joint replacement, while effective in reducing pain and improving function, shows varying long-term mortality outcomes, suggesting the need for further research into how different surgical procedures impact patients' activity levels and overall well-being.

Objectives: i) To compare the volume and intensity of physical activity 15 years after surgery in patients after hip resurfacing and total hip replacement and ii) to explore the association between the participants' physical activity and functional outcome scores.

Study design: A cross-sectional observational (follow-up) study.

Study population: We will approach patients that have previously participated in a randomised controlled trial during which they received either hip resurfacing ($n = 34$) or total hip replacement ($n = 26$).

Intervention (if applicable): In this study there is no intervention, only observation using accelerometers. Participants will be asked to complete four physical activity questionnaires. Subsequently, they will wear a tri-alaxial accelerometer on their non-dominant wrist continuously for ten days and nights, and simultaneously wear a tri-axial accelerometer taped to the surgical thigh for a period of 48 hours.

Main study parameters/endpoints: Using the accelerometers we will measure the participants' physical activity energy expenditure (PAEE), the intensity distribution of PAEE and step count. Secondary outcomes include self-reported physical activity, health status and the ability to perform specific activities.

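### Section 10.1 reduces the accelerometer signal to one value per minute before deriving step count, so this main endpoint would be a model prediction and not a count of steps

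*Combined protocol and SAP*

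**What the plan says.** The Summary of the combined protocol and SAP lists the main endpoints: "Using the accelerometers we will measure the participants' physical activity energy expenditure (PAEE), the intensity distribution of PAEE and step count". Section 8.1.1 assigns PAEE and its intensity distribution to both devices and step count to the wrist device alone: "The wrist worn GENEActiv triaxial accelerometer will additionally measure the participants' step count".

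Section 10.1 gives one processing order for the wrist and thigh data. The signal is calibrated against gravity, the three axes are combined into a single vector magnitude (VM), and non-wear time is excluded. Then: "The acceleration signal will be summarised to a common time resolution of one observation per minute and subjected to prediction models". The sentence runs on over a page break: "to calculate physical activity energy expenditure, time in moderate-to-vigorous physical activity, and step count".

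The next paragraph of 10.1 names software: "Raw accelerometry data will be processed using the R-project for Statistical Computing and open-source packages". The documents give no step algorithm, no sampling frequency, no definition of the per-minute summary, no list of inputs to the step model, and no separate route to steps from the unaggregated signal.

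**The concern.** A one-minute summary is a workable basis for PAEE and for time in an intensity band, because both are quantities accumulated over time. A step is a discrete event lasting about half a second to a second. Once a minute is represented by one number, the oscillation that identifies each step is gone, and a later model can only infer a number of steps from how much the wrist accelerated on average.

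Two things are at stake. First, the endpoint would not be what sections 8.1.1 and the Summary describe: readers would take a measured count from what is a modelled proxy. Second, the proxy would be built from the same kind of minute-level acceleration summary as PAEE, so the two endpoints would tend to move together for reasons of construction. That limits what step count adds to the comparison of resurfacing with total hip replacement.

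**Working it through.** The plan states no figure for this point, so there is nothing to reproduce. Three checks follow.

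**1. Resolution needed and resolution kept.**
- From section 10.1: 1 observation per minute. Assumed: cadence of 60 to 120 steps per minute.
- Highest frequency resolvable at a sampling rate f is f/2. At 1 per minute this is 0.5 cycles per minute, or 0.5/60 = 0.0083 Hz.
- Step frequency is cadence/60: 60/60 = 1 Hz up to 120/60 = 2 Hz.
- Samples needed exceed 2 × cadence: 2 × 60 = 120 up to 2 × 120 = 240 per minute.
- Individual steps therefore cannot be detected after the summary.

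**2. One synthetic minute, before and after the summary.** The signal was VM = 1 + 0.2·sin(2π·(c/60)·t) in g, up to a fixed phase shift, sampled at an assumed 50 Hz with the same amplitude at every cadence c.

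| Cadence (steps/min) | Minute mean VM (g) | Minute mean of the absolute value of VM − 1 (g) | Peaks detected at 50 Hz |
|---|---|---|---|
| 60 | 1.000 | 0.127 | 60 |
| 90 | 1.000 | 0.127 | 90 |
| 120 | 1.000 | 0.127 | 120 |

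The value 0.127 is 0.2 × 2/π, which does not depend on c. Detection before aggregation recovers the count exactly in this clean signal. Equal amplitude is an assumption. If amplitude rises with cadence, the minute value carries some indirect information on cadence, but the steps themselves are still not observed.

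**3. Illustration of the link with PAEE.** 100 simulated samples of 60 people, with 1,440 minute values x each. Assumed gamma distributions (shape, scale) were:
- walking minutes per day (4, 20) and other active minutes (4, 50);
- minute signal while walking (6, 20), in other activity (3, 20) and at rest (1, 3).

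Cadence was normal with mean 100 and SD 10, independent of the signal. The PAEE signal is the daily sum of x. True steps are cadence × walking minutes.

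| Daily steps taken as | Mean correlation with PAEE signal (5th to 95th percentile) |
|---|---|
| Linear, 0.9x summed | 1.00 (by construction) |
| Saturating, 120x²/(x² + 80²) summed | 0.999 (0.998 to 0.999) |
| Threshold, 100 steps for each minute with x > 80 | 0.964 (0.948 to 0.978) |
| True steps | 0.597 (0.467 to 0.738) |

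The sizes depend on the assumed distributions. They show how steps predicted from minute values can follow PAEE much more closely than true steps do; they are not an estimate for this cohort.

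**The case against.** The strongest reply is that 10.1 is one compressed sentence covering two devices and three outputs. It does not define what an observation is. It could hold several features, including a cadence feature computed from the raw signal, and a per-minute step total is itself at one-minute resolution. The software sentence speaks of raw data, and section 8.1.1 cites sources for step count. All of this is possible, and the authors may intend it. But VM is the only signal named, no cadence feature is described, and neither a software name nor a citation changes the stated order. If separate pipelines are meant, the text still has to say so.

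Other parts of the reply stand and limit the point:

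- A reader might infer that step count would carry no information beyond PAEE. The documents do not support that. Sums over days of a non-linear prediction need not preserve ranks, extra inputs would separate the two further, and section 8.1.1 has PAEE measured by both devices, so it need not rest on the wrist signal alone.
- A reader might infer that agreement between steps and PAEE will be presented as independent confirmation. No section says this.
- The ratio of 120 to 240 is not a measure of harm. It shows that steps cannot be detected one by one; it gives no error in daily steps or in the group difference.
- A reader might attribute errors from walking aids or a still arm to the one-minute summary. The documents report nothing on walking aids or arm swing, and wrist-based detection on the raw signal shares that weakness.
- Nothing is lost at data collection.

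**Conclusion.** The point holds for the plan as written. Following 10.1 in its stated order yields a prediction of steps from minute-level acceleration, whereas section 8.1.1 promises a measurement and the Summary makes it a main endpoint. The resolution argument rests only on the one-minute summary in 10.1 and an assumed cadence of 60 to 120 steps per minute; any plausible cadence gives the same conclusion. A strong correlation with PAEE is likely, at 0.96 to 1.00 in the illustration, but that range rests on assumed distributions and on a model driven by the minute signal alone. The effect on the implant comparison cannot be sized from the documents.

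This is a defect in the written processing order, not in the data to be collected. It should be corrected, preferably before any data are seen. It does not undermine PAEE or intensity, which address the primary objective directly. The conclusion would weaken if the authors confirmed that a step or cadence feature is computed from the raw signal before the summary.

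**What to change.** In section 10.1, separate the two routes:

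- **Steps:** name a step-detection algorithm and its version, state the sampling rate, and say that it runs on the calibrated wrist signal at that native rate before any aggregation. Detected steps are then summed to minutes and days.
- **PAEE and intensity:** keep the one-minute summary and the prediction models, for these outputs only.

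Optionally, derive steps from the raw thigh signal over the 48 hours when both devices are worn and compare them with the wrist count. Wrist detection can still miss steps when arm swing is reduced, and only this comparison would show it. It covers 2 of the 10 wrist days, so it serves as a check and not as a replacement.

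The cost is some extra computing and one more algorithm to name. The recorded data are already to be downloaded and stored, so nothing changes for participants.
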